### Patient Engagement

Arm 1: Point of Care (POC). Patient engagement in the POC arm will involve approaching patients completing routine visits (either in-person or through telemedicine). We will either use electronic tablets in the waiting room or walk the patient through the questions over the phone to screen for familial cancer risk. Patients flagged as high risk based on simple personal or family cancer history will go on to be offered genetic testing (see Testing below).

Arm 2: Direct Patient Engagement (DPE). Patient engagement in the DPE arm will involve contacting patients by mail and email. The outreach will provide a link to the online familial cancer risk screening tool. If flagged as high risk, patients will be offered genetic testing (see Testing below).

**Note: The three components below are included to provide additional context and describe the clinical procedures that will be taking place as part of normal, recommended practice. These are not research procedures.**

### Provider and Staff Engagement

Training will be provided on genetics and guidelines for high risk patients. This training will consist of webinars and online materials and will include Continuing Medical Education (CME) credits, to encourage participation. In addition, [name], an investigator on this study, will be available for consult via phone or email to assist with any questions related to genetic testing and patient care recommendations.

### Clinic Engagement

To ensure that patients with abnormal results receive appropriate follow-up care, we will guide participating clinics in creating a system to organize and systemize the follow-up care. While each of the clinics may tailor the workflows to specific clinical needs, the core components of follow-up will be similar across participating clinics including education and support of the providers involved in care; changes to the EMR to cue providers and patients of the needs for care; and up-to-date guidelines support for options such as chemoprevention and changes in screening frequency and/or type.

### Testing

Patients who complete the risk assessment questionnaire and are found to be high risk should be offered genetic testing. This recommendation is part of standard clinical guidelines. Patients in the POC arm will be sent an email with more information and will be connected to the Color Genomics website to complete genetic testing, if desired.

Patients in the DPE arm will be sent from the risk assessment questionnaire directly to a site with more information and connected to the Color Genomics website to complete genetic testing, if desired. For the genetic testing, a testing kit will be mailed to the patient. Three to four weeks later, results will be sent to the patient and their provider.

### Follow-up Assessment

The study will track how many patients complete the risk assessment questionnaire and how many complete genetic testing.

Approximately 12 months after the initial baseline assessments, another random sample of patients and all of the providers and the clinic leader at each clinic will be asked to complete a survey. The survey will take approximately 20 minutes to complete and will be done online or on paper. Reminders to complete the survey will be sent by email and/or mail. A subset of providers will be interviewed. As with the baseline interview, the interviews will be performed over the phone and will be recorded so that the transcripts can be analyzed.

### Process Analysis

To obtain feedback on the risk assessment and genetic testing process, and determine what factors play into a patient's decision making along the way, we will interview samples of patients who have reached various stages. One sample will be taken from those patients who are not interested in completing the risk assessment (e.g., select the "skip survey" option in the risk assessment or decline to complete it when approached by clinic staff in the POC clinics). A second sample will be from those who complete the risk assessment. A third will be from patients who are eligible for the genetic testing, but decide not to complete it. And a final sample will be taken from patients who complete the genetic testing process. Interviews will be completed by phone and recorded.

As an additional level of analysis, we will survey participants who ordered a genetic testing kit but did not complete it. The survey will ask about the testing process, their reasons for ordering a kit and why they didn't return it, general thoughts about genetic testing, and a section of demographics (age, sex, education, etc). A paper copy of the survey will be mailed to these participants, in addition to email outreach. The survey may be completed on paper or online.

### Previvor Activities

All patients who test positive for one or more mutations will discuss their testing process with a trained interviewer during an interview before they receive results, and at 6 months after they receive results. In addition, we will invite previvors to complete a survey (separate from the baseline assessment that a random sample received) and an interview. These will be done at separate time points from the other follow up assessments as previvors will be identified at varying intervals (as they test). The assessment will be administered at baseline (when they first receive their results) and at 6 months post-results. The interviews will happen in conjunction with the assessments, at a time the patient and interviewer arrange. For previvors we have uploaded into zipline the previvor report, a document that is meant to help patients understand what their next steps are. And, we have uploaded a document detailing the measures that we will use with previvors at baseline, before they receive the results, and at 6 months post results receipt.

### Aim 4 Activities

Providers, clinic staff, and clinic leaders will be sent a link to an anonymous REDCap survey via email that will ask them about their individual effort and time spent launching and maintaining the study at their respective clinics.

Providers, clinic staff, and clinic leaders will be asked for their email once the survey is completed if they wish to proceed with follow-up. Their emails will be stored with their results once they opt-in for follow-up.

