## OVERVIEW

### **Objectives**

The purpose of this study is to determine how to best implement appropriate genetic testing and follow-up care in the primary care setting.

**Aim 1:** Compare two strategies for identifying members of a primary care clinic's population who have a family or personal history of cancer and encouraging these high-risk individuals to obtain genetic testing for cancer susceptibility mutations. The two methods are: 1) Point of Care (POC) approach, completed in conjunction with a regularly scheduled appointment; and 2) Direct Patient Engagement (DPE), using letters and emails. Individuals will be asked to visit a web site for screening for family/personal history of cancer. Genetic testing will be recommended for those determined to be high risk. Outcomes will be the fraction of the clinic population that participates in the family/personal screening and the fraction of the clinic population that undergoes genetic testing.

Hypothesis 1: DPE screening will result in a higher proportion of active patients who screen for familial cancer risk compared with POC screening.

Hypothesis 2: Of screened patients, POC patients will produce a higher proportion of tested patients compared with DPE.

**Aim 2:** Identify changes, problems, and inefficiencies in clinical flow and interactions during and after the implementation of genetic testing.

**Aim 3:** Evaluate the effects of the two methods of implementation on patient, provider, and health system leader reports of benefits and harms, satisfaction, and perceived quality of care.

**Aim 4:** Evaluate the value (cost-effectiveness) and affordability (budget impact) of each method.

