#### **Aim 3**

A random sample of active patients will be selected from each clinic and asked to complete a baseline survey. This sample will come out of the list of patients who meet the eligibility criteria defined in section 2.2. The clinic or a healthcare system representative will pull the contact information for the selected patients from their electronic medical record (EMR). The study staff will reach out using mail and email. Outreach materials will clearly state the role of the clinic in the study and as the source of the patient's contact information (see attached Study Recruitment Templates). This process will be repeated approximately 12 months later, to obtain a second snapshot of the patient population.

We are also interested in interviewing patients who have reached various stages in the risk assessment and genetic testing process. The patient names and contact information will be obtained by clinic staff or directly from the patient through the risk assessment survey.

For previvors (patients who test positive for one or more mutations) we receive the results from Color Genomics from patients who have agreed to allow Color to share their results and we implement the previvor assessment and intervention procedures, using email and telephone.

Providers, clinic staff, and clinic leaders at each clinic will be identified by a representative at the clinic. All of these individuals will be contacted. Contact information will come from the clinic's employee directory or a similar source. Outreach will be conducted using mail and email and will clearly state the role of the clinic in the study and as the source of the individual's contact information (see attached Study Recruitment Templates). A random sample of those who agree to be interviewed will be contacted for an interview.

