#### **Aim 4**

This aim will include the providers, clinic staff, and clinic leaders at each clinic that were identified in Aim 3. All of these individuals will be contacted. Contact information will come from the clinic's employee directory or a similar source. Outreach will be conducted using email to complete a longitudinal survey. Emails will be collected at the end in order to follow-up.

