### **Payment to participants**

Participants will be compensated for survey and interview time using gift cards provided by the research team. They will receive the gift cards (\$50 for providers and clinic leaders in Aim 3, \$10 for patient surveys and baseline previvor interviews, \$20 for patient follow-up previvor interviews, and \$10 for providers, staff and clinic leaders in Aim 4) within a month after each completed interview or survey.

The typical amount a patient would receive is \$10 (for completing a single survey). The typical amount a provider would receive is \$50 (for completing a single survey). The greatest total amount a participant could receive is \$240 (a provider completing the baseline survey and interview, at \$50 each, the follow-up survey and interview, at \$50 each, and all 4 economic surveys, at \$10 each).

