### **Non-monetary compensation**

High risk patients will receive genetic testing at no cost to them and those who complete the testing will have access to free genetic counseling. Providers and staff will have access to free CME credits as part of completing training provided by the study.

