### **Anticipated direct benefits to participants**

Patients found to be at high risk will have access to genetic testing and genetic counseling. The study will cover the cost of these activities.

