## **STATISTICAL ANALYSIS PLAN**

The primary outcomes are the fraction of the clinic population that participates in the risk assessment screening and the fraction of the clinic population that undergoes genetic testing. We will look at how well the interventions did in terms of getting people to be screened and tested, and how it varies across clinics within treatment arms.

The outcomes are binary, i.e., whether or not each individual in the clinic population completed screening or genetic testing, and individuals are clustered within clinics. Only a minimal amount of identifying data will be required for the screening (ex: age, sex), therefore we plan to analyze two sets of data. The first includes data collected in aggregate at the clinic site level and the second includes data collected at the patient level and integrated additional data at the site level. Analyses of the primary outcomes will use the clinic as the unit of analysis, with the outcome variable for each clinic being the percent of that clinic's population who complete the screening assessment. We will perform a series of bivariate logistic regression models with scale adjustment for overdispersion. We will also use multivariable logistic regression to estimate and test the relative odds between the study arms for the primary outcomes.

We will estimate the value (cost effectiveness) of one screening strategy over the other, using the incremental cost effectiveness ratio (ICER) to determine which strategy provides more value for the investment made. We will express each of these outcomes as the cost per patient screened and the cost per patient tested.

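### Aim 4's staff-time survey, as described, would mix research hours with the cost of delivering each method, and the SAP does not say which other costs enter

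*Combined protocol and SAP*

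**What the plan says.** The Objectives section sets Aim 4 as: "Evaluate the value (cost-effectiveness) and affordability (budget impact) of each method".

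The Aim 4 paragraph under Recruitment and Screening limits the respondents to clinic personnel: "This aim will include the providers, clinic staff, and clinic leaders at each clinic that were identified in Aim 3". Aim 4 Activities says that they will be asked about their "individual effort and time spent launching and maintaining the study at their respective clinics". Payment to participants refers to "all 4 economic surveys", so the survey is repeated. No other data collection is described for this aim.

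On testing and counselling, Non-monetary compensation states: "High risk patients will receive genetic testing at no cost to them and those who complete the testing will have access to free genetic counseling". Anticipated direct benefits to participants adds: "The study will cover the cost of these activities". Follow-up Assessment says that the numbers screened and tested will be tracked.

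The economic part of the Statistical Analysis Plan opens: "We will estimate the value (cost effectiveness) of one screening strategy over the other". It names the ICER, expressed per patient screened and per patient tested. It gives no perspective, time horizon or list of cost components, and it does not mention budget impact.

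**The concern.** The thing being costed in the survey description is the study, not the engagement method. A clinic that later adopted POC or DPE would not draw research samples, supply baseline data to investigators or sit for research interviews. Hours spent on those tasks do not belong in the cost of either method. Self-reported hours that are not divided when they are collected are hard to divide afterwards.

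A second gap concerns costs that clinic personnel never see. The study pays for testing and counselling. Mailings, tablets and contact by study staff are part of delivery and differ between arms. A survey of clinic staff time prices none of these, and the SAP does not say whether or how they enter.

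At stake are the Aim 4 results a health system would use to choose between methods and to budget. The primary outcomes are not affected.

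**Working it through.** The plan states no cost, ICER or budget figure, so there is nothing to reproduce. The check sets the passages side by side and then uses cost identities.

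**1. Research-only work placed on clinics**

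- Contact details for the random patient sample are pulled by the clinic or a health-system representative, and again about 12 months later (Aim 3, under Recruitment and Screening).
- A clinic representative identifies the personnel to be surveyed (same section).
- Clinics supply aggregate data before randomization (Baseline Assessment).
- Personnel complete baseline surveys, and a subset are interviewed. Providers and the clinic leader are surveyed again at about 12 months, with a subset of providers interviewed (Baseline Assessment, Follow-up Assessment).

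Nothing in the documents separates these hours from delivery hours.

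**2. Effect on the cost measures**

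For arm a, let D be delivery staff cost, R research staff cost, T patients tested and S patients screened. The cost collected is D + R.

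- Staff cost and its share of budget impact are overstated by R in each arm.
- Cost per patient tested is overstated by R/T, and cost per patient screened by R/S.
- The ICER numerator is (D_DPE − D_POC) + (R_DPE − R_POC). If R is the same in both arms, the second term is zero.

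Near-equality of R is plausible. Half of the 12 clinics go to each arm, the baseline tasks precede randomization, and the 12-month tasks apply to every clinic. The documents give no hours, so R cannot be given a value.

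**3. Effect if a cost P per tested patient were left out**

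P is the test charge plus average counselling cost per tested patient, assumed equal in both arms. Write dC for the difference in other costs, dT for extra tests and dS for extra screens.

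- Cost per patient tested is too low by P in each arm. The difference between arms in that average is unchanged.
- ICER per extra test: (dC + P × dT)/dT = dC/dT + P, so it is too low by P.
- ICER per extra patient screened shifts by P × dT/dS.
- Total budget is too low by P × T.

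Number of Subjects anticipates around 3,000 tests. The documents give no price, so P is assumed:

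| Assumed P | 3,000 × P |
|---|---|
| $100 | $0.30 million |
| $250 | $0.75 million |
| $500 | $1.50 million |

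**4. An invented example, to show that direction can change**

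Suppose POC has 1,200 tests and $200,000 staff cost, and DPE has 1,800 tests, $120,000 staff cost and 5,000 more patients screened. Then dT = 600 and dS = 5,000.

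- Staff cost only: dC = 120,000 − 200,000 = −$80,000. DPE costs less and tests more (−80,000/600 = −$133 per extra test; −80,000/5,000 = −$16 per extra screen).
- With P = $250: −80,000 + 250 × 600 = +$70,000, or $117 per extra test and $14 per extra screen. The shifts are 250 and 250 × 600/5,000 = 30, as the identities require.
- The sign changes at P = 80,000/600 ≈ $133.

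**5. The two effects together**

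If both occurred, the net error in an arm's cost per patient tested would be R/T − P. They act in opposite directions, and the documents do not show which is larger.

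**The case against.** Aim 4 Activities summarises the survey in one sentence. The questionnaire is not in the public file, and Data Collection refers to a measures document that is also not included. The items may already separate delivery from research. This stands, and it limits the conclusion to what the stated wording would produce.

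The research load may also be light. Contact pulls may fall to a health-system representative, one person per clinic identifies personnel, and most of the roughly 250 planned personnel have no stated research task beyond paid surveys and interviews. This is a fair reason not to put a percentage on the overstatement. It does not show that the overstatement is zero.

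Three stronger readings are tempting, and the documents do not support them:

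- *Tests and counselling are excluded from the costs.* Test counts are tracked, the study as payer should hold the charges, and the SAP never limits the ICER to staff time. What is missing is a stated unit cost, a record of counselling use and a rule for including them. Who would pay outside the study depends on perspective, which is not stated.
- *Research time in POC alone distorts the ICER.* Process Analysis gives patients who decline when approached by POC staff as one example, beside those who choose the skip option. Aim 3 says "The patient names and contact information will be obtained by clinic staff or directly from the patient", and the sentence goes on to name the risk assessment survey as the patient's own route, which needs no clinic staff.
- *The SAP drops the value of each method.* An ICER needs each arm's cost and effect, and the SAP names cost per patient screened and per patient tested. Only budget impact is unaddressed.

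**Conclusion.** The point holds in a limited form. Hours collected under the wording in Aim 4 Activities would include research time and overstate each method's staff cost and budget impact. The size cannot be estimated from the documents. The ICER numerator would be largely protected, on the assumption that research time is similar in the two arms.

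The missing perspective, cost components and budget-impact method are a secondary matter of incomplete specification. The consequence of leaving out P is exact for the ICER per extra test and for each arm's cost per patient tested, given an equal P in both arms. Counselling is optional, so P could differ between arms. The dollar totals rest on an assumed price.

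A reader might infer that the Aim 4 results will not be the cost of running POC or DPE. The documents support only that they cannot be shown to be that cost. The change should be made, but this does not threaten the trial's main comparison.

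**What to change.** **Main change.** Have each Aim 4 survey record hours separately for (a) delivering the engagement method and follow-up and (b) research tasks, with the tasks listed in step 1 of the working as examples of (b). Enter only (a) in cost per patient screened, cost per patient tested, the ICER and budget impact. If the items already do this, say so in Aim 4 Activities and in the SAP.

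**Clarification in the SAP.** State the perspective. State that study-funded testing and counselling enter the costs, together with delivery costs outside clinic staff time (mailings, tablets, study-staff contact with patients), and give the source of each. Add a budget-impact analysis for each method.

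**Cost.** A slightly longer survey, retrieval of charges that the study should already hold as payer, a record of counselling use, and a few sentences of SAP text. The split of hours has to be in place when the surveys are fielded.

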### **Data Collection**

We are asking for general approval of the surveys and interviews that will be completed by participants. The topics are described below and more detail can be found in the uploaded EDGE Measures Table document.

The risk assessment questionnaire completed by all active patients asks about their personal cancer history as well as that of any relatives (cancer type, age at diagnosis, relationship to patient). It also asks if any family member has had a mutation in a cancer gene identified. The surveys completed at baseline and throughout the course of the study by samples of patients will provide additional information about the clinic's patient population in regard to demographics, quality of life, satisfaction with care, genetic literacy and self-efficacy, feelings about genetic testing, trust in their provider and the healthcare system, and familial communication. The patient interviews will assess the engagement approach and the patient's reasons for responding (or not responding). We will also ask about the potential benefits and harms associated with each step of the risk assessment and genetic testing process. The provider/staff baseline survey will cover the organization's leadership and readiness for change. Providers will be asked about their background and training, and about their genomic confidence and self-efficacy. The second survey at 12m will reassess provider's genomic confidence and self-efficacy. The provider/staff baseline interview will ask about perspectives on the clinic and healthcare system in regard to risk assessment and genetic services, intervention characteristics (e.g., evidence strength & quality), and the external climate. The interviews at 12m will cover their evaluation of the testing process and clinical activities related to results provision.

The most sensitive questions we will ask (in relation to the previvor assessments) are as follows:

1. Identities of marginalization
  - a. Questions about feeling a part of a group or feeling like the participant is getting the resources that they need
2. Level of coercion during process of participation and source
  - a. During the testing process did you feel pressure from staff or providers to give a sample for genetic testing?
3. Areas of concern due to positive results (morbidity, mortality, financial stress, discrimination, QOL)
  - a. Do you have any concerns about your health now that you have a positive mutation result?
4. Perceived barriers of PGx (pharmacogenomics) in Primary Care
  - a. Do you perceive you will have challenges managing your medication and accessing medication?
5. Level of influence from PCP in decision to participate
  - a. Did you work with your provider during or after the testing process?
6. Self-rated level of distress from positive result
  - a. How do you feel right now? Any changes since you got your mutation findings?

7. Modalities used for self-direct information gathering
  - a. Do you have any thoughts about the testing process?
8. Utilization rate of PGx in Primary Care
  - a. Will you inquire about prophylactic treatments with your PCP as a result of your results?

